8.5. SPONSOR	14
8.6. FUNDING	14
8.7. AUDITS	15
9. STUDY MANAGEMENT	15
10. PUBLICATION POLICY	15
11. REFERENCES	15

GLOSSARY OF ABBREVIATIONS

CIV	Common iliac vein
MTS	May Thurner Syndrome
DVT	Deep vein thrombosis
IVUS	Intravascular Ultrasound
CFV	Common femoral vein

KEYWORDS

Common Iliac Vein (CIV) May-Thurner Syndrome (MTS) Duplex Ultrasound

STUDY SUMMARY

TITLE The use and reproducibility of duplex ultrasound to provide indices of left Common Iliac Vein (CIV) diameter, for improved diagnosis of May Thurner Syndrome (MTS) in patients presenting with unexplained left leg swelling.

DESIGN Feasibility/Pilot Study.

AIMS To investigate the use and reproducibility of duplex ultrasound to determine diameter indices of left CIV compression.

OUTCOME MEASURES The diameter measurement of the left CIV in adults, and the inter- and intra-operator variation of the diameter measurement of the left CIV using duplex ultrasound.

POPULATION Adult patients referred to the vascular ultrasound department.

ELIGIBILITY Patients with or without venous disease, who have not had previous treatment for iliac vein disease.

DURATION 9 months

REFERENCE DIAGRAM

[if appropriate]

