1. INTRODUCTION

1.1. BACKGROUND

May Thurner Syndrome (MTS) is a vascular condition whereby the left common iliac vein (CIV) becomes compressed between the right common iliac artery and the spine. This condition is often asymptomatic, however MTS can cause severe left lower limb complications such as swelling, pain, oedema, reflux, varices, skin changes and deep vein thrombosis (DVT). It is thought that approximately 2-3% of lower limb DVT's are caused by MTS, however there is an almost 56% predominance for left sided DVT suggesting this number is underestimated and cases of MTS are regularly missed (Peters et al., 2012). DVT can be a serious medical condition and can go on to cause pulmonary embolism, a sometimes fatal condition if not identified and treated quickly and effectively.

Diagnostic imaging studies such as ultrasonography, venography and intravascular ultrasound (IVUS) are used to evaluate the CIV and identify the site and severity of any narrowing that is present. Duplex ultrasound is often the first line of imaging as it is risk free, cost effective, and accurate at identifying lower limb venous insufficiency. However the location of the iliac veins deep in the abdomen has limited its use for identifying specific features of MTS. It is also highly operator dependent and the results obtained may be dependent on the experience level of the vascular scientist performing the scan. Abdominal ultrasound scans are also always performed with the patient lying completely flat, however this does not reflect the haemodynamic changes that occur within the venous system when a patient is standing. Indirect measurements can be taken to help indicate if there is an iliac vein obstruction, such as interrogation of the common femoral vein (CFV) to assess phasicity and reflux. However, these readings can suggest proximal problems but do not differentiate between compression and thrombus.

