2. STUDY OBJECTIVES

The primary objective of this study is to investigate diameter variation of the left CIV based on posture in adults referred to the vascular ultrasound department, using duplex ultrasound.

The secondary objective of this study is to determine inter- and intra-observer variation of the diameter measurement of the left CIV using duplex ultrasound, in adults referred to the vascular ultrasound department.

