3. STUDY DESIGN

The study will be a feasibility/pilot study lasting approximately six months, recruiting 40 patients from the vascular ultrasound department at Imperial College Healthcare NHS Trust. 20 patients will be symptomatic for lower limb venous disease and 20 patients will be asymptomatic. The following outlines the timeline of events for the patients recruited onto the study.

OUTPATIENT APPOINTMENT

At their outpatient appointment patients who may be eligible to take part in the study will be identified and approached. Patient notes and GP referral letters will be read prior to seeing the patient in the outpatient appointment, to identify suitable participants. Suitable participants will be those that will be requiring a vascular ultrasound scan in the vascular ultrasound department. The study will be explained and if the patient gives verbal consent to receiving study information material, then this will be given to the patient for consideration. They will be told that formal consent will be taken at their scan appointment if they agree to partake in the study and that if they choose not to partake this will not affect their usual clinical care. Participants will be given up to six weeks to decide if they would like to take part.

TELEPHONE CALL

Patients will be contacted two weeks after their outpatient appointment to enquire as to whether they would like to take part in the study. Those that decline will have their scan request form passed on to the department receptionist for booking in the usual way. Those that would like to take part in the study will have a date and time arranged to come to the department to have their scan as part of the study, followed by the scan requested by the clinical team. The study scan and the routine scan will be made on the same day to avoid the patient having to come to the hospital multiple times. Some patients from the symptomatic group may have been referred for this type of scan.

[figure not shown]
ULTRASOUND SCAN APPOINTMENT

Order of events at the scan appointment will be as follows;

[figure not shown]
- Eligibility check and formal consent - 5 minutes
- Recording of demographic details and medical history - 5 minutes
- The patient will have their routine scan performed as requested by the referring clinician - Between 30 and 90 minutes, dependent on the scan type requested.

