- A clinical vascular scientist will perform the study ultrasound scan and take three readings of the left CIV with the patient lying flat and three readings of the left CIV with the patient at a 45 degree angle on a tilted examination couch - 10 minutes
- Two further clinical vascular scientists will perform the same study scan and take the same readings - 20 minutes
- Patient will be thanked for their time and a routine follow up appointment will be made with the referring clinician.

The below flow chart illustrates this order of procedures:

Prior to the ultrasound scan appointment:

During the ultrasound scan appointment:

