3.1. STUDY OUTCOME MEASURES

The primary outcome measure is the diameter variation ranges of the left CIV in adults referred to the vascular ultrasound department.

The secondary outcome measure is the inter- and intra-operator variation of the diameter measurement of the left CIV using duplex ultrasound, in adult patients referred to the vascular ultrasound department.

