7. STATISTICS AND DATA ANALYSIS

The sample size has been calculated using a sample size calculator assuming a prevalence of 2%, confidence level of 95% and margin of error of 5%. This calculation gives a sample size of 31. This sample size is in line with a previous study by Mousa et al. (2016) which had a sample size of 36.

A one-way ancova test will be performed to assess the difference in iliac vein diameter between the two groups. An intraclass correlation coefficient will be used to measure intra- and inter-observer reliability. Support will be provided from the Imperial Statistics Services during the analysis phase.

Statistics and data analysis aspects of the study have been reviewed by [name], the academic supervisor at Manchester Metropolitan University.

Data and all appropriate documentation will be stored for a minimum of 10 years after the completion of the study, including the follow-up period.

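### The primary objective in Section 2, change in left CIV diameter with posture, has no matching analysis in Section 7, and the protocol does not state one primary aim

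*Combined protocol and SAP*

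**What the plan says.** Section 2 sets the main question: "The primary objective of this study is to investigate diameter variation of the left CIV based on posture in adults". The scan appointment in Section 3 is built to supply the data. One vascular scientist takes three readings with the patient flat and "three readings of the left CIV with the patient at a 45 degree angle on a tilted examination couch", and two more scientists then repeat the same scan.

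The other statements of aim do not mention posture. Section 3.1 says: "The primary outcome measure is the diameter variation ranges of the left CIV in adults referred to the vascular ultrasound department". The outcome measures in the Study Summary begin with "The diameter measurement of the left CIV in adults", and the aims listed there concern diameter indices and reproducibility. In Section 1.2 the research question is about diameter ranges that could help diagnosis, and the first objective is to image the vein.

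On groups, Section 3 says "20 patients will be symptomatic for lower limb venous disease and 20 patients will be asymptomatic". Section 7, the only statistics section, gives a sample size of 31 from a prevalence calculation and then two analyses. The first is "A one-way ancova test will be performed to assess the difference in iliac vein diameter between the two groups". The second is an intraclass correlation coefficient (ICC) for intra- and inter-observer reliability. No covariate is named for the ANCOVA, although the appointment includes "Recording of demographic details and medical history".

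**The concern.** A posture effect is a contrast within a patient: the same vein, flat and tilted. The ANCOVA in Section 7 is a contrast between patients, and the ICC describes agreement among readings. Followed as written, the study would take flat and tilted readings from every patient and report no flat-to-45-degree estimate, and no interval, for the objective that Section 2 calls primary.

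Because the statements of aim differ, a reader cannot tell whether the primary result should be a posture difference, a set of diameter ranges or a group comparison. That leaves room for the choice to be made once results are visible.

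**Working it through.** **1. The plan's own figure.** Section 7 gives a prevalence of 2%, 95% confidence and a 5% margin. The single-proportion formula is n = z² p(1 − p) / d² = 1.96² × 0.02 × 0.98 / 0.05² = 30.12, rounded up to 31. The stated figure reproduces. It concerns the precision of a prevalence and says nothing about diameter or posture, so it does not reveal an intended posture analysis.

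**2. Data collected.** 3 operators × 3 readings × 2 postures = 18 readings per patient, 9 in each posture. Flat and tilted readings come from the same patient and are paired.

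**3. Does either planned analysis estimate the posture change?**
- *ANCOVA between groups.* Write the mean diameter in group g and posture p as m + G(g) + P(p). The group difference in either posture is G(1) − G(2). The posture term, common to both groups, cancels.
- *ICC.* This addresses agreement within and between observers, which is the secondary objective. It does not give a mean flat-minus-tilted difference.
- *The two groups read as the two postures.* The only two groups that the design defines are symptomatic and asymptomatic patients. On this reading a one-way ANCOVA would also treat paired readings as independent.
- *Flat diameter as the unnamed covariate.* The plan does not say so, and the test would still compare patient groups.

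No paired comparison, posture term or descriptive posture summary appears elsewhere in the document.

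**4. Precision available from a paired estimate.** Average each patient's readings over operators within each posture and take flat minus 45 degrees. In units of the standard deviation (SD) of that within-patient change, the 95% confidence interval half-width is t(0.975, n − 1) / √n:
- n = 40: 2.023 / 6.325 = 0.320 SD
- n = 20, one group: 2.093 / 4.472 = 0.468 SD
- Difference in change between two groups of 20: t(0.975, 38) × √(2/20) = 2.024 × 0.316 = 0.640 SD

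The documents give no SD. If the SD of the change were 1, 2 or 3 mm (an assumed range), the half-width would be 0.32, 0.64 or 0.96 mm overall, and 0.47, 0.94 or 1.40 mm within a group.

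These figures need usable readings in both postures from every patient. Section 1.1 notes that the depth of the iliac veins has limited ultrasound here, so some loss is possible. With 31 usable pairs, for example, the overall half-width is 0.367 SD.

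**The case against.** The strongest reply is that posture is only one of several statements of aim. Section 2 alone names it as an objective. Section 1.2 also criticises earlier work for studying symptomatic patients only, and Section 3 recruits equal groups with and without symptoms, so the ANCOVA serves a stated rationale. This stands. A reader might infer that the group comparison is a stray analysis that must become secondary. The documents do not support that; its rank depends on which aim is chosen.

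Sections 2 and 3.1 both speak of variation in diameter, so the outcome can be read as an abbreviated form of the objective. That is fair: the wording is incomplete, not plainly contradictory. It still leaves Section 7 without a posture analysis, or any planned ranges, on either reading.

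A reader might also take the remark in Section 1.1 about flat scanning, that "this does not reflect the haemodynamic changes that occur within the venous system when a patient is standing", as the declared reason for the posture objective. That is an inference. The remark is general background about standing, whereas the study tilts patients to 45 degrees.

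Finally, this is a feasibility/pilot study, both postures and the number of readings are fixed in advance, and statistical support is promised. The pilot status means that no powered test is needed. It does not remove the need to say how the primary objective will be estimated. The support is promised for the analysis phase, which does not pre-specify anything.

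**Conclusion.** The point holds. The plan gives no result for the primary objective in Section 2, because the one diameter analysis in Section 7 targets a different contrast and the ICC serves the secondary objective. The protocol also lacks a single primary aim across the Study Summary and Sections 1.2, 2 and 3.1.

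Three stronger conclusions might be drawn, and the documents do not support them:
- That the study cannot answer the posture question. The paired readings are planned for every patient, so nothing is lost if the analysis is added.
- That the primary result will be chosen after the data are seen. This is a risk left open by the text, not a certainty.
- That the half-widths measure an error. They show the precision that a paired estimate could have: about 0.32 SD with 40 usable pairs and 0.47 SD within a group of 20. They do not say how far any planned result is wrong.

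The unnamed covariate, and the silence on which posture supplies the ANCOVA diameter, are real but lesser gaps in specification. They add little to the main point.

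**What to change.** Reconcile the Study Summary and Sections 1.2, 2 and 3.1 so that they state one primary aim and one matching primary outcome.

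In Section 7:
- Add a posture analysis. For each patient, average the readings over operators within each posture, then report the paired flat-minus-45-degree difference with a 95% confidence interval. No hypothesis test is required in a pilot.
- Report diameter ranges by posture and group, with the number of patients who have usable readings in both postures.
- Keep the symptomatic versus asymptomatic comparison, using one mean per patient for each posture, and rank it according to the reconciled aim.
- As a minor point, name the covariate from the data recorded at the appointment, or call the comparison unadjusted.

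The cost is wording in those sections and slightly more analysis work. No new patients or readings are needed.

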1.2. RATIONALE FOR CURRENT STUDY

More widespread use of ultrasound for examining the iliac veins would be beneficial as it may avoid the need to expose patients to the invasive procedures requiring radiation and contrast agents that are necessary for venography and IVUS. Previous studies examining duplex ultrasound and iliac veins, as mentioned above, have examined the use of velocity ratios, interrogation of the CFV and examination of phasicity but have not investigated using ultrasound to measure the absolute diameter of the CIV. There is currently no definitive diameter that the CIV can be considered compressed or not compressed. All of the previous studies used symptomatic patients only and so it cannot be assumed that the results would correlate in asymptomatic patients. Also, it is known that ultrasound is highly operator dependent but none of the previous studies examined the impact of this on measuring the CIV diameter. Therefore, further work needs to be carried out to assess the use of ultrasound for imaging the left CIV and aiding MTS diagnosis.

The principle research question is whether duplex ultrasound could be used to image the left CIV and investigate diameter ranges that can help in the diagnosis of MTS. The first objective is to use duplex ultrasound to image the left CIV in a cohort of patients referred to the vascular ultrasound clinic. The second objective is to determine inter- and intra-observer variation of the diameter measurement of the left CIV using duplex ultrasound. The hypothesis is that ultrasound can be used to image left CIV compression and the measurements obtained during the examination are highly reproducible both within an operator and between operators.

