If the results of this research study find that ultrasound can be used to image the left CIV, can define 'normal' diameter ranges and is a reproducible diagnostic tool, then this could reduce the time taken for patients presenting with symptoms of MTS to be diagnosed. Ultrasound is a quick and readily available imaging tool, and so creating an appropriate scanning protocol will enable regular scanning and screening of patients who may have this condition. As well as aiding diagnosis it should also help reduce the number of patients with this condition that go on to suffer from further severe complications such as DVT. These results should also help identify which patients need to go on to have the more invasive tests and rule out patients that do not require them. Iliac vein scanning with ultrasound is not routinely performed in all vascular departments across the country, with many only taking indirect measurements from the CFV's. If a benefit is found to doing this scan then it could be introduced to many more/all departments, benefiting many more patients.

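### Operator variation in the left CIV diameter is to be summarised only by an ICC of unstated form, and the plan does not commit to reporting measurement error or between-operator differences in mm

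*Combined protocol and SAP*

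**What the plan says.** Section 2 sets the secondary objective: to "determine inter- and intra-observer variation of the diameter measurement of the left CIV using duplex ultrasound". Section 3.1 repeats it: "The secondary outcome measure is the inter- and intra-operator variation of the diameter measurement of the left CIV using duplex ultrasound". Neither gives a unit or a statistic.

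Section 7 is the only analysis text. It names a one-way ANCOVA for the difference in diameter between the two patient groups, which does not address operators. For operators it says: "An intraclass correlation coefficient will be used to measure intra- and inter-observer reliability". It does not state the model, agreement or consistency, single or averaged readings, a confidence interval or a threshold. No section mentions a within-patient SD, standard error of measurement, repeatability coefficient, mean difference between operators or limits of agreement.

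Section 1.2 gives the purpose. It observes that "none of the previous studies examined the impact of this on measuring the CIV diameter" (operator dependence), wants to "investigate diameter ranges that can help in the diagnosis of MTS", and hypothesises that "the measurements obtained during the examination are highly reproducible both within an operator and between operators". The hoped-for benefit depends on ultrasound being able to define normal "diameter ranges and is a reproducible diagnostic tool".

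Section 3 plans the data: 40 patients (20 symptomatic, 20 asymptomatic), each scanned by three vascular scientists, with three readings lying flat and three at 45 degrees from each scientist. It does not say whether the same three scientists scan every patient.

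**The concern.** A diameter is a length, and the study wants ranges of that length to inform a diagnosis. Someone applying such a range needs to know how far a repeat reading, or a colleague's reading, may differ in mm. The ICC sets error variance against the spread between patients, so it can be high because the scans are precise or because the patients are very different. This sample deliberately combines symptomatic and asymptomatic patients. If their diameters differ, the ICC rises with no gain in measurement precision.

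If section 7 is followed to the letter, the study could conclude that the measurement is highly reproducible without giving readers what they need to judge a diameter range. It could also leave a systematic offset between operators undisclosed.

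**Working it through.** **Inputs.** From section 3: 40 patients, 3 operators, 3 readings per operator per posture. From section 7: an ICC, form unstated. The documents give no SD of CIV diameter, so every SD below is an assumption that shows scale and is not an estimate for this trial.

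**1. The plan's own figure.** Section 7 derives 31 patients from prevalence 2%, 95% confidence and a 5% margin: 1.96² × 0.02 × 0.98 / 0.05² = 30.12, rounded up to 31. It reproduces. It concerns the precision of a proportion and does not bear on operator variation.

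**2. Same ICC, different error in mm.** For a single-reading absolute-agreement ICC, all non-patient variance counts as error, so the standard error of measurement is SEM = SD_total × √(1 − ICC). The 95% difference between single readings by two operators (reproducibility) is 1.96 × √2 × SEM = 2.77 × SEM. With ICC = 0.90, √(1 − 0.90) = 0.316:

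| Assumed total SD (mm) | SEM (mm) | 95% between-operator difference (mm) |
|---|---|---|
| 1.5 | 0.47 | 1.31 |
| 3 | 0.95 | 2.63 |
| 5 | 1.58 | 4.38 |

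Same-operator repeatability is a different and smaller quantity. Suppose the variance shares are patient 90%, operator 1%, patient-by-operator 3% and residual 6%. Then the inter-observer ICC is 0.90 and the one-way intra-observer ICC is 93/99 = 0.94 at every SD. Same-operator repeatability, 2.77 × SD_total × √0.06, is 1.02, 2.04 or 3.39 mm at the three SDs. This is algebra: rescaling the SD leaves both ICCs unchanged and scales the errors in mm.

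**3. Same error in mm, different ICC.** With SEM fixed at 1 mm (95% difference 2.77 mm), ICC = SD_b² / (SD_b² + 1). For a between-patient SD (SD_b) of 1, 2, 3 or 4 mm it is 0.50, 0.80, 0.90 or 0.94.

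**4. The unstated form matters.** Assume between-patient SD 3 mm, error SD 1 mm and operators offset by −2, 0 and +2 mm. The variance of the offsets is (4 + 0 + 4)/2 = 4.
- Consistency ICC: 9 / (9 + 1) = 0.90. The offsets have no effect.
- Absolute-agreement ICC: 9 / (9 + 4 + 1) = 0.64. The offsets lower the value, but their size and direction are not shown.

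**5. The planned readings can supply the missing quantities.** With all 40 patients measurable, one operator's within-patient SD in one posture has 40 × (3 − 1) = 80 degrees of freedom. The 95% CI factors √(80/χ²) are 0.866 and 1.183. The approximate relative half-width is 1.96/√(2 × 80) = 16%. If only 31 patients were measurable, it would be 1.96/√(2 × 62) = 18%.

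For an operator pair, let S_d² be the variance of the paired differences of three-reading means, and s1² and s2² the two within-operator variances. A single-reading difference has variance V = S_d² + (2/3)(s1² + s2²). The SE² of a limit of agreement is S_d²/40 + 1.96² × Var(V)/(4V), with Var(V) = 2S_d⁴/39 + (4/9)(2s1⁴/80 + 2s2⁴/80). Assume reading SD 1 mm and full data:
- Patient-by-operator SD 0: S_d² = 0.667, V = 2, half-width of the 95% CI (t on 39 df) 0.28 × SD of differences.
- Patient-by-operator SD 2 mm: S_d² = 8.667, V = 10, half-width 0.49 × SD of differences.

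**The case against.** The ICC is a standard statistic for observer reliability, and sections 2 and 3.1 say only variation, with no unit. Section 7 can fairly be read as defining that variation as reliability. The ICC is also computed from variance components in mm. Because the primary outcome is the range of diameters, the spread should be known once the data are in, and an absolute-agreement ICC with the matching SD gives an SEM in mm. This is also a pilot, with statistical support promised for the analysis phase.

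Much of this stands. A reader might infer that an ICC can never yield an error in mm, or that the secondary outcome would go unreported. The documents support neither: the first ignores the back-calculation, and the second reads a unit into the objective that is not there.

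What remains is that the plan commits neither to the absolute-agreement form nor to the matching SD, and the back-calculation needs both. Even then, offsets between particular operators would not be shown. The promise of statistical support names no analysis. Pilot status does not remove the gap either, because operator variation is a stated objective here.

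**Conclusion.** The point holds as a gap in the analysis plan, and it should be fixed. The planned ICC is legitimate but incomplete for a study aiming at usable diameter ranges, and alone it supports the reproducibility hypothesis only weakly. The same value of 0.90 is compatible with 95% between-operator differences from about 1.3 to 4.4 mm over assumed total SDs of 1.5 to 5 mm.

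Two further inferences should be resisted. The figures do not show that the measurement is poor, because the SDs are assumed. Nor is the design at fault: the replicate readings suffice, although precision falls if some veins cannot be imaged, and section 1.1 itself notes that their depth limits ultrasound.

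**What to change.** Amend section 7, using the readings already planned and analysing each posture separately:

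- (a) For each operator, report the within-patient SD and the same-operator repeatability coefficient (2.77 × SD) in mm, with 95% CIs.
- (b) For each operator pair, report the mean difference and the 95% limits of agreement in mm for single readings, with 95% CIs, using all three readings and allowing for the repeats (V above). If the scientists vary between patients, use instead a mixed model with patient, operator, patient-by-operator and residual terms.
- (c) Plot difference against mean to check whether error changes with vein size. If it does, report on a log or percentage scale, since a single figure in mm would then mislead.
- (d) Keep the ICC as supportive, with 95% CI and its form stated: two-way absolute-agreement single-reading for inter-observer, one-way single-reading for intra-observer.

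Base the reproducibility conclusion mainly on (a) and (b). Stating an acceptable error in mm beforehand is desirable but optional in this pilot, because section 1.2 says: "There is currently no definitive diameter that the CIV can be considered compressed or not compressed".

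Cost: a few sentences in section 7 and some extra tables. No new scans, staff or patients are needed.
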